7.4 Measures to be Taken to Avoid or Minimize Bias

This study is designed as a stratified, randomized, controlled clinical trial to minimize bias in both assigning patients to treatments and in analyzing the results. Each clinical site is limited to a maximum number of patients (as described in Section 11.1: Sample Size) to minimize bias that may be introduced if the majority of patients are enrolled at

one or two clinical sites. In addition, the study will utilize uniform definitions for study endpoints.

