11.0 Statistical Considerations

11.1 Sample Size

The expected rates of adjunctive therapy for the Enforcer balloon and conventional angioplasty groups were assumed to be 5% and 15%, respectively. A sample size of at least 250 total lesions (125 lesions per group) is required to detect a 10% difference in the rate of adjunctive therapy with a power of 80% and a type I error of 0.05. Prior experience suggests that 40% of patients, on average, would also have a second lesion treated. Therefore the study will enroll approximately 200 patients (approximately 100 patients per group) and enrollment will continue until at least 250 lesions are treated. Procedural outcomes are unlikely to depend on the connectivity between lesions within an AV dialysis access circuit or the patient-level factors which affect longer-term outcomes, and therefore lesions were assumed to be independent for the purposes of the sample size calculation.

Up to 10 clinical sites will be included in the study, and the maximum enrollment per clinical site will be no more than 80 patients or 40% of the total enrollment. There is no minimum enrollment threshold. Patients that withdraw from the study will not be replaced.

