11.2 Randomization

Once patient eligibility is confirmed, patients will be randomized into either the Enforcer balloon or conventional angioplasty group prior to treatment in a 1:1 ratio at each study site. Randomization will be first stratified by the number of lesions requiring treatment (single lesion or two lesions) and type of AV access circuit (fistula or graft). Using restricted randomization maximizes the balance of treatment allocations within stratum and vice versa. Randomization codes will be maintained by the Sponsor.

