11.3 Analyses

11.3.1 Primary endpoint analysis

The study is intended to compare the necessity of adjunctive therapies for lesions treated with the study device (Enforcer balloon) compared to those treated with the control device (conventional angioplasty balloon inflated to standard pressures). The null (H_0) and alternative (H_A) hypotheses are expressed as follows:

$H_0: AT_{EB} \geq AT_{CA}$

$H_A: AT_{EB} < AT_{CA}$

where AT_{EB} is the rate of adjunctive therapies in the Enforcer balloon group and AT_{CA} is the rate of adjunctive therapies in the conventional angioplasty balloon group.

The rates of adjunctive therapies will be compared between the two treatment groups with a one-sided Z-test. A p-value $< .05$ will be used to claim statistical significance. If the number of patients within each strata are sufficiently large, the association of stratification factors and treatment will be assessed. Crude and adjusted, if applied, differences in rate of adjunctive therapies between the two treatment groups and 95% confidence intervals will be reported.

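### The primary test ignores the randomisation strata, and the optional adjusted analysis has no threshold, method or trigger; one prespecified stratified, patient-clustered comparison would settle this at N = 250

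*Combined protocol and SAP*

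**What the plan says.** Sections 7.4.1 and 11.2 randomise patients 1:1 at each site, stratified by number of lesions (one or two) and access type (fistula or graft), which gives four strata apart from site. Section 11.2 states the purpose: "Using restricted randomization maximizes the balance of treatment allocations within stratum and vice versa". Section 7.4 says that the stratified, randomised, controlled design serves "to minimize bias in both assigning patients to treatments and in analyzing the results".

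Section 11.3.1 sets the confirmatory analysis: "The rates of adjunctive therapies will be compared between the two treatment groups with a one-sided Z-test". A p-value below .05 "will be used to claim statistical significance". The strata have no part in that test. The section continues: "If the number of patients within each strata are sufficiently large, the association of stratification factors and treatment will be assessed". It then says that crude differences, and adjusted ones where adjustment is carried out, will be reported with 95% confidence intervals.

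The strata are used more explicitly elsewhere. Section 11.3.2 makes them regression covariates for the secondary endpoints. Section 11.3.3 explores their effect on the additional measures between the groups. Section 11.5 leaves site out of the primary analysis.

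**The concern.** Three things in Section 11.3.1 are unsettled.

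- **The object of the assessment.** Taken at its word, the sentence relates the stratification factors to treatment. Restricted randomisation within strata fixes that relation at about zero, so the result says nothing about adjunctive therapy. The useful questions are whether the strata predict the outcome and whether the treatment effect differs between them.
- **The condition.** No stratum size is given, and the smallest stratum may well be judged too small. A comparison pooled over strata needs no such condition.
- **The adjusted difference.** No method, covariates or trigger are named. A second estimate of the primary effect could therefore appear, or not, once the data are known.

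What is at stake is some precision, and above all a primary analysis that is fixed in advance.

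**Working it through.** **Inputs from the plan.** Section 11.1: adjunctive-therapy rates of 5% (Enforcer) against 15% (control); 80% power and alpha 0.05; for the lesion count, "A sample size of at least 250 total lesions (125 lesions per group) is required to detect a 10% difference"; 40% of patients have a second lesion treated; lesions are taken as independent for the sample size. Section 11.3.1: one-sided test at .05.

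**Assumptions (not in the plan).** Graft share, adjunctive-therapy risk by stratum, and within-patient correlation rho.

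**1. The plan's own figure.** With pooled variance, one-sided 0.05 and 80% power:

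n = [1.645·√(2·0.10·0.90) + 0.842·√(0.05·0.95 + 0.15·0.85)]² / 0.10² = (0.698 + 0.352)² / 0.01 ≈ 110.2, so 111 per group.

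At 125 per group the same formula gives 84.2% power (exact enumeration of the Z-test: 86.2%). A one-sided Fisher exact or continuity-corrected test has 79.8% at 125 per group, which matches the stated 80%. So 250 lesions is adequate for the one-sided test on the plan's own assumptions.

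**2. Stratum sizes.** 250 / 1.4 ≈ 179, so take 180 patients, with 20% grafts assumed.

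| Stratum | Patients | Lesions per arm |
|---|---|---|
| Fistula, one lesion | 180·0.6·0.8 = 86.4 | 43 |
| Fistula, two lesions | 180·0.4·0.8 = 57.6 | 58 |
| Graft, one lesion | 180·0.6·0.2 = 21.6 | 11 |
| Graft, two lesions | 180·0.4·0.2 = 14.4 | 14 |

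The last stratum has about 7 patients per arm.

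**3. What the crude test loses.** With balanced arms the crude and stratified estimates nearly coincide, but the crude standard error still contains the between-stratum variance. For independent lesions and stratum weights w:

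SE ratio (stratified / crude) = √[Σ w·p(1−p) / (p̄(1−p̄))]; actual size of the crude test = 1 − Φ(1.645 / ratio).

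Example, 10% in fistulas and 35% in grafts: p̄ = (101·0.10 + 25·0.35)/126 = 0.1496; total variance 0.1272; within-stratum variance (101·0.09 + 25·0.2275)/126 = 0.1173; ratio √0.922 = 0.960; 1.645/0.960 = 1.713; size 0.043.

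| Assumed risks | Graft share of lesions | SE ratio | Size of crude test |
|---|---|---|---|
| 8 / 12% | 30% | 0.998 | 0.050 |
| 8 / 15% | 30% | 0.994 | 0.049 |
| 5 / 20% | 30% | 0.972 | 0.045 |
| 5 / 25% | 25% | 0.957 | 0.043 |
| 10 / 35% | about 20% | 0.960 | 0.043 |
| 5 / 10 / 35 / 45% | about 20% | 0.924 | 0.0375 |

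For the last row p̄ = 18.1/126 = 0.1437, total variance 0.1230 and within-stratum variance 13.23/126 = 0.1050. Simulation of the layout in step 2 agrees: crude size 4.3% and 3.7% in the last two rows, against 5.0% for Cochran-Mantel-Haenszel, with crude 95% interval coverage of 95.6% and 96.5%. Power in the most extreme case is 86.7% crude and 88.0% stratified, a gap of 1.3 points. With strata that are not prognostic and rates of 5% against 15%, it is 86.5% and 86.4%.

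**4. What stratifying alone does not repair.** Patients are randomised but lesions are counted. With 40% of patients contributing two lesions, the design effect is [0.6 + 0.4·2·(1 + rho)] / 1.4 = 1 + 0.571·rho, and the size is 1 − Φ(1.645 / √design effect).

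| rho (assumed) | Design effect | Size at nominal 0.05 |
|---|---|---|
| 0.1 | 1.06 | 0.055 |
| 0.3 | 1.17 | 0.064 |
| 0.5 | 1.29 | 0.073 |

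Simulated at lesion level, rho 0.3 gives 0.060–0.064 crude and 0.062–0.064 stratified; rho 0.5 gives 0.070–0.074 and 0.073–0.075.

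**5. The choice of test.** With independent lesions, a Wald test on the Mantel-Haenszel risk difference with the simple unpooled variance runs at about 5.4–5.5% in the two strongly prognostic settings. The variance estimator therefore has to be named.

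**The case against.** The strongest reply is that the sentence is merely loose. It stands next to the adjusted difference, Section 11.3.2 uses the strata as covariates, and Section 11.3.3 looks at their effect on outcomes between groups. A strata-by-treatment assessment of the outcome may well be what is meant. That is plausible, but Section 11.3.1 does not say it, and the remedy is the same: write it down.

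The second reply is that the effect is small, runs in the conservative direction and depends on stratum risks that the plan does not give. This stands in full. Even in the extreme case both analyses keep more than the planned 80% power.

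Four stronger readings are tempting, and the documents do not support them:

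- **That no adjusted primary result is planned.** Section 11.3.1 allows one. It is optional and unspecified, not absent.
- **That leaving out the strata biases the estimate or raises type I error.** Under balanced allocation it does neither; the crude test becomes slightly conservative.
- **That Section 7.4 promises a stratified test.** It describes the design as a whole and makes no such commitment.
- **That stratifying by itself yields the right standard error.** It does not if the two lesions of one patient are correlated. Section 11.1 argues for independence, but invokes it only for the sample size.

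**Conclusion.** The point holds as one of specification, with a modest gain in precision. The confirmatory test does not use the factors on which patients were randomised, and the only routes by which they enter the primary analysis are conditional and undefined. For strongly prognostic strata the crude test's size is about 4.3% or 3.7% instead of 5%, with about 1 point of power given up. For weak or absent prognostic effects there is nothing material to gain or lose. These figures rest on assumed graft shares and stratum risks and on independent lesions. The direction does not depend on the exact values; the size does. The better reason to act is that the form of the adjusted primary result is left open until the data are known. Any replacement must deal with paired lesions as well, since their possible effect (size 0.055 to 0.073 for rho 0.1 to 0.5) runs the other way and stratification leaves it in place.

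**What to change.** In Section 11.3.1, replace the sentence on stratification factors and the one on crude and adjusted differences with one prespecified primary analysis:

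- A risk difference, test and confidence interval stratified by lesion number and access type as randomised, carried out whatever the stratum sizes.
- A patient-clustered variance, with the estimator named. One example is a Mantel-Haenszel-weighted risk difference whose variance comes from the spread between patients within stratum and arm, with the n − 1 divisor because the smallest stratum may hold about 7 patients per arm.
- The crude difference and its interval always reported beside it, as supportive.
- If heterogeneity is to be examined, a statement that this means treatment-by-stratum on adjunctive therapy, and that it does not decide which analysis is primary.

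A supportive model with baseline percent stenosis and lesion length, which Section 9.1 already records, is optional.

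The cost is plan wording and programming. No new data are needed and N stays at 250. When the strata are not prognostic, stratifying costs about 0.1 point of power (86.5% against 86.4%). If lesions within a patient do prove correlated, the clustered interval will be wider than the crude one. That reflects the data and is not a cost of the change.

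### Does reporting 95% confidence intervals beside a one-sided 0.05 Z-test leave the primary claim undecided?

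*Combined protocol and SAP*

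**What the plan says.** Section 11.3.1 sets a directional null and alternative: the Enforcer rate of adjunctive therapy is at least that of conventional angioplasty, or it is lower. The rates are "compared between the two treatment groups with a one-sided Z-test", and the next sentence makes p < .05 the criterion for claiming significance. Crude and, if applied, adjusted "differences in rate of adjunctive therapies between the two treatment groups and 95% confidence intervals will be reported". The section does not say whether those intervals are one- or two-sided, and gives them no part in the decision.

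Section 11.1 takes rates that "were assumed to be 5% and 15%, respectively" for Enforcer and conventional balloons, and states: "A sample size of at least 250 total lesions (125 lesions per group) is required to detect a 10% difference", "with a power of 80% and a type I error of 0.05". It gives no side and no test version. It adds that "lesions were assumed to be independent for the purposes of the sample size calculation". On recruitment it says: "Prior experience suggests that 40% of patients, on average, would also have a second lesion treated". From this it derives about 200 patients, with enrollment continuing until at least 250 lesions have been treated. Section 7.1 gives the same 250-lesion minimum as the end of enrollment.

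**The concern.** A one-sided test at 0.05 rejects beyond 1.645 standard errors, whereas a two-sided 95% interval excludes zero only beyond 1.96. Results between the two produce a superiority claim printed beside an interval that contains no difference. A reader who judges by the interval would think the claim unsupported.

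The unspecified continuity correction matters near the boundary, because the same data can pass one version of the Z-test and fail the other. The silence of 11.1 on the side of its 0.05 also raises the question of whether the sample size was computed for the test that 11.3.1 performs.

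Finally, the step from a 40% second-lesion rate to about 200 patients is not the arithmetic the text implies. If these gaps left the primary decision open, the trial's main conclusion could depend on choices made after the data were seen.

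**Working it through.** **Inputs.** Rates 5% and 15%, 125 lesions per group, 80% power, type I error 0.05, independent lesions and a 40% second-lesion rate (all 11.1); one-sided Z-test at p < .05 (11.3.1).

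**1. The plan's sample size.** Per group, with pooled variance and no correction:

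n = [z_α √(2 × 0.10 × 0.90) + 0.8416 √(0.05 × 0.95 + 0.15 × 0.85)]² / 0.10²

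- One-sided 0.05 (z = 1.645): (0.698 + 0.352)² / 0.01 = 110.2, so 111.
- Two-sided 0.05 (z = 1.960): (0.832 + 0.352)² / 0.01 = 140.1, so 141.
- One-sided with continuity correction: 128 (unpooled) or 130 (pooled).
- All two-sided versions tried (pooled, unpooled, arcsine, corrected): 133 to 160.

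Only one-sided 0.05 is compatible with 125. Power at 125 per group:

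- Uncorrected, by formula: (0.10 − 1.645 × 0.03795) / 0.03742 = 1.004, giving 84.2%.
- Full enumeration of the 126 × 126 outcomes: 86.2% uncorrected, 79.8% continuity-corrected, 79.8% Fisher exact.

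So 11.1 and 11.3.1 agree, and 125 per group delivers about 80% or more under either version of the planned test.

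**2. Can the claim and the interval diverge?** Take 8/125 vs 17/125. The difference is 0.072, the pooled SE 0.03795 and the unpooled SE 0.03767.

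- Uncorrected: z = 0.072 / 0.03795 = 1.897, p = 0.029.
- Corrected: z = (0.072 − 0.008) / 0.03795 = 1.687, p = 0.046. Fisher exact: p = 0.045.
- Wald 95% interval: 0.072 ± 1.960 × 0.03767, or −0.2 to 14.6 points. The 90% interval is 1.0 to 13.4.

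So yes. Probability of a claim beside a two-sided 95% interval that includes zero, by enumeration:

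| Z-test / Wald interval | 5% vs 15% | 8% vs 15% | 10% vs 10% |
|---|---|---|---|
| uncorrected / uncorrected | 7.8% | 11.6% | 2.5% |
| corrected / corrected | 10.0% | 12.0% | 1.6% |
| corrected / uncorrected | 1.4% | 3.0% | 0.4% |

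**3. Does the divergence affect error control?** The claim depends on p alone. At 10% in both groups, total false-positive claims are 5.2% (uncorrected) or 3.1% (corrected). Across equal rates of 5% to 15% the ranges are 5.0% to 5.6% and 2.4% to 3.5%. The interval does not enter these figures.

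**4. Does the unspecified correction matter?** For 8/125 vs 16/125, p = 0.043 uncorrected and 0.066 corrected. The versions disagree in 6.5% of trials at 5% vs 15%. The corrected statistic is always the smaller, because 1/125 is subtracted from the numerator over the same SE. Every corrected rejection is therefore also an uncorrected one. Choosing the more favorable of the two after seeing the data would simply reproduce the uncorrected test, with the 5.2% above.

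**5. Would a 90% interval do better?** It removes every case of a claim beside an interval that includes zero. It is not a full cure: a corrected Z-test beside an uncorrected 90% Wald interval gives the reverse conflict (no claim, interval excludes zero) in 6.5%, 9.2% and 2.2% of trials for the same three rate pairs. In that pairing the 95% interval disagrees with the test less often.

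**6. Patients.** 250 / 1.4 = 178.6, about 179 patients; 200 × 1.4 = 280 lesions, and 280 / 250 = 1.12. With 200 patients, 250 lesions are still reached if only 25% have a second lesion (200 × 1.25 = 250).

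**The case for a change.** The case for a change is that it costs a few sentences and no patients. Pairing the claim with a 90% interval or a one-sided 95% bound, using the same correction as the test, would stop a claim from appearing beside an interval that includes zero. Naming the Z-test version in advance would settle borderline tables such as 8/125 vs 16/125. The sample size adds some ambiguity: 80% at 125 per group matches a corrected or exact test, while a plain reading of Z-test suggests the uncorrected one.

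The facts in this argument stand. The inference that readers would not know which result governs does not, because 11.3.1 states the p-value rule directly after naming the test and says only that intervals are reported. Nor does the text call the interval two-sided; a one-sided 95% bound would agree with the test, apart from the small difference between pooled and unpooled variance. Clearer labeling would help presentation, but it would not alter the primary decision rule.

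**Conclusion.** No change follows. Taken exactly as written, the plan has a directional hypothesis, a named test and one explicit threshold, and 125 lesions per group support that test with 79.8% to 86.2% power. A two-sided 95% interval beside a one-sided 0.05 test is a common descriptive choice. It would look discordant in 1.4% to 10.0% of trials at the design rates, but it neither creates nor cancels a claim.

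The missing side in 11.1 is supplied by 11.3.1 and confirmed by the sample size. The unspecified correction is a gap an analyst can fill either way, with a false-positive rate of about 5% or below (at most 5.6% over the equal rates examined). The 200-patient figure is a planning approximation about 12% above what the plan's own second-lesion rate implies, and the 250-lesion stopping rule makes it immaterial.

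These figures assume exactly 125 lesions per group, Wald intervals, and independent lesions as 11.1 does. Whether independence is justified is a separate question that this point does not address.

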11.3.2 Analysis of secondary endpoints

Differences in pain, procedural costs, procedure times, and maximum balloon pressure will be assessed overall by one-sided t-tests, with Enforcer balloon having favorable outcomes. In addition, regression models will be used to incorporate the stratification factors as covariates and reported if found to be significant. If the parametric assumptions are not met, nonparametric methods will be used. The safety claim will be evaluated with a Z-statistic, with a non-inferiority of Enforcer balloon at a margin of 10%. The observed non-inferiority margin will also be presented.

Adjustments for multiplicity will be made using the Holm procedure to control the family-wise error rate to 0.05 across the family of secondary endpoints.

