9.3 Study Procedure

PTA with either the Enforcer balloon or conventional angioplasty balloon will be performed and recorded in accordance with the manufacturer's IFU to achieve a residual stenosis < 30%. The balloon diameter may be chosen based on the recommendations in the IFU. If necessary, the balloon could be deflated, repositioned, and re-inflated to achieve a residual stenosis < 30%. Inflation details (e.g., maximum pressure and duration of inflations) will be recorded on an appropriate eCRF. Conventional angioplasty balloons are defined as those having a rated burst pressure less than 25 atmospheres. Completion angiography to assess percent residual stenosis of the treated study lesion(s) should be performed immediately following the study procedure (initial treatment with Enforcer or conventional angioplasty balloon) and prior to beginning any adjunctive procedures.

The physician may also perform adjunctive procedures (e.g., using a high-pressure balloon, cutting balloon, stent, or stent graft) if in the best interest of the patient. High-pressure angioplasty balloons are defined as those having a rated burst pressure greater than or equal to 25 atmospheres. The adjunctive procedure may be performed in accordance with the device manufacturer's IFU to achieve a residual stenosis < 30%. Completion angiography following any adjunctive procedures should also be performed. Any additional procedures performed will be documented on the appropriate eCRF.

All angiographic images and medical charges (i.e., UB-04 or CMS-1500) should be provided to the Sponsor on the appropriate eCRF. Total procedure time (defined as the time from needle entry for intervention to sheath withdrawal) as well as total procedural charges will be recorded on the appropriate eCRFs.

Type(s) and level(s) of sedation provided during the procedure will be recorded on the appropriate eCRF. A single assessment representing the pain associated with balloon inflations during the procedure is recommended to be recorded at or before the time of the patient's discharge assessment. Patients will be instructed to rate the pain they feel

using a numeric pain rating scale (0-10, where 0 indicates no pain and 10 indicates the worst possible pain). A summary of the procedure is given in Table 9.3-1 below.

Table 9.3-1. Procedure requirements

Procedure	
Assessment(s)/ Procedure(s)	Perform angioplasty according to study randomization

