	Perform adjunctive procedures (as needed to achieve less than 30% residual stenosis, or if in the best interest of the patient) 
• If applicable, an additional completion angiography should be performed
	Record lesion treatment information on the appropriate eCRF, such as: 
• Post-treatment lesion % stenosis• Balloon information, including inflation(s), duration(s), and maximum balloon pressure(s)
	Complete patient-reported pain assessment
	Provide total procedural charges

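### Four secondary endpoints are tested without adjustment after stratified allocation, and the adjusted result is reported only if significant

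*Combined protocol and SAP*

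**What the plan says.** Sections 7.4.1 and 11.2 stratify patients by number of lesions (one or two) and access type (fistula or graft) and randomise them 1:1 within each site, using restricted randomisation. The block size is not stated.

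Under section 11.3.2, differences in pain, procedural costs, procedure times and maximum balloon pressure "will be assessed overall by one-sided t-tests, with Enforcer balloon having favorable outcomes". As an addition, "regression models will be used to incorporate the stratification factors as covariates and reported if found to be significant". The section does not say whether the treatment effect, a covariate or the whole model must be significant, and it does not name site. The fallback is: "If the parametric assumptions are not met, nonparametric methods will be used". No method or trigger is given. Multiplicity is handled "using the Holm procedure to control the family-wise error rate to 0.05 across the family of secondary endpoints".

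On the unit of analysis, section 9.3 makes pain one value per patient ("A single assessment representing the pain associated with balloon inflations during the procedure"). It also defines a total procedure time, which "as well as total procedural charges will be recorded on the appropriate eCRFs". Table 9.3-1, however, lists maximum pressures under lesion treatment information, and section 11.1 notes: "Prior experience suggests that 40% of patients, on average, would also have a second lesion treated". Section 11.3.2 states no unit for maximum pressure.

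Two other sections matter. Section 11.3.1 reports crude and, if applied, adjusted differences with 95% intervals for the primary endpoint, with no significance condition. Section 11.3.3 explores the stratification variables for the additional measures and again reports only if a test suggests a difference. Section 11.5 leaves site out of the primary analysis; no section adds it for the secondary endpoints.

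**The concern.** Stratified allocation balances the arms on lesion number, access type and site, so differences between strata add almost nothing to the true variability of the treatment difference. An unadjusted t-test still counts that variance in its standard error. The standard error is then too large, the test rejects too rarely under the null, and power is lost. The loss is greater at the smaller alpha of the first Holm step.

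The reporting rule is a separate matter. If the adjusted estimate appears only when something in the model is significant, the published set of adjusted results is selected on the data. This holds however much variance the factors explain.

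Two gaps bear on any repair. If maximum pressure is analysed with lesions as rows, two lesions from one patient would be treated as independent, and the error could go the other way. And an unnamed fallback lets the data influence which p-value enters Holm.

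**Working it through.** **Plan's own figure.** The plan gives no SD, effect size or power for these endpoints. Its only power figure is for the primary endpoint (125 lesions per group, 5% v 15%, 80%). A one-sided Fisher exact test reproduces it at 79.8%; it has no bearing here.

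**Inputs.** From the documents: about 200 patients, 1:1, up to 10 sites, two binary factors, 40% with two lesions, one-sided tests, family-wise 0.05. Assumed: the share of variance explained by strata and site (R2) at 0, 0.1 and 0.3, and an effect of 0.353 SD, which gives about 80% power when R2 = 0.

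**Step 1: one value per patient, by formula (exact balance).**
- Crude standard error: √(4/200) = 0.1414 SD. True standard error: 0.1414 × √(1 − R2), that is 0.1342 at R2 0.1 and 0.1183 at R2 0.3.
- Size of the crude test: 1 − Φ(1.645/√(1 − R2)) = 5.0%, 4.2%, 2.5% at R2 0, 0.1, 0.3.
- Crude power: 1 − Φ((1.645 × 0.1414 − 0.353)/true SE) = 80.3%, 81.5%, 84.6%.
- Adjusted power: 1 − Φ(1.645 − 0.353/true SE) = 80.3%, 83.8%, 91.0%.

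**Step 2: the same by simulation.** Ten equal sites, blocks of 4 within site × lesion number × access type, 30% grafts, explained variance half site and half the two factors (all assumed); 6,000 runs per setting; Monte Carlo SE about 0.3 points for size and 0.3 to 0.6 for power.

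| R2 | Size: crude | Size: adjusted with site | Power: crude | Power: two factors | Power: with site |
|---|---|---|---|---|---|
| 0 | 4.6% | 4.6% | 79.5% | 79.3% | 79.0% |
| 0.1 | 4.1% | 4.6% | 80.5% | 81.6% | 82.6% |
| 0.3 | 2.7% | 4.6% | 82.9% | 87.0% | 90.5% |

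The gain is 82.6 − 80.5 = 2.1 points at R2 0.1 and 90.5 − 82.9 = 7.6 at R2 0.3. At R2 0 the loss is 79.5 − 79.0 = 0.5. Repeats with 4,000 and 3,000 runs gave gains of 1.8 and 2.5 points, then 6.9 and 7.4, with crude size 3.9% and 3.0 to 3.1%. With about 200/40 = 5 patients per cell, balance is imperfect, which is why simulation and formula differ slightly.

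If the six bullets of section 7.5.2 were six tests, the first Holm step would use 0.05/6. Crude v adjusted power is then 51.8 v 56.4% at R2 0.1 and 52.2 v 70.7% at R2 0.3.

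**Step 3: choosing between results.** Rejecting when either the crude or the site-adjusted test is significant had size 4.9%, 4.9% and 4.8%.

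**Step 4: maximum pressure with lesions as rows.** With 120 one-lesion and 80 two-lesion patients there are 280 rows. The variance inflation is 1 + ρ × ((120 × 1 + 80 × 4)/280 − 1) = 1 + 0.571ρ, or 1.171, 1.286 and 1.400 at an assumed within-patient correlation ρ of 0.3, 0.5 and 0.7.
- Ordinary adjusted regression: 1 − Φ(1.645/√inflation) = 6.4%, 7.3%, 8.2%. Simulated: 6.2%, 7.1%, 8.2%.
- Crude t-test, inflation × (1 − R2): 5.5%, 6.3%, 7.1% at R2 0.1 and 3.5%, 4.2%, 4.8% at R2 0.3. Simulated: 5.4%, 6.1%, 7.1% and 4.3%, 4.6%, 5.3%; a repeat gave 5.2 to 7.0% and 4.3 to 5.7%.
- Highest value per patient, adjusted: simulated size 4.9 to 5.1%.

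**Step 5: skewed cost** (lognormal, log-SD 0.9 assumed), power at R2 0.1/0.3: crude t 66.5/67.1%; linear adjusted 68.4/74.3%; crude rank test 79.2/81.4%; regression on ranks 81.1/88.7%, with size 4.8%. The choice of method matters enough to be fixed in advance.

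**The case against.** The strongest reply is that this is largely a matter of efficiency. An overall t-test after stratified allocation is valid, these are secondary endpoints with no power target, and the benefit depends on an R2 that the documents do not supply. The larger figures need R2 = 0.3 with half of it assigned to site; the 0.05/6 figures also assume six tests and describe only the first Holm step. All of this stands, and it limits the weight of the adjustment argument. It does not touch the reporting rule, the missing unit or the open fallback, which are defects even at R2 = 0.

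Three stronger readings are tempting and should be resisted.
- A reader might infer that the plan ignores the stratification factors. It does not: section 11.3.2 plans a regression on both. The weakness is its supplementary status, the absence of site and the conditional reporting.
- A reader might infer that conditional reporting inflates type I error. The crude tests are not conditional and, read naturally, are the ones that enter Holm. Even rejecting on either result kept size below 5% in Step 3.
- A reader might take 6 to 8% as the plan's error for maximum pressure. That range belongs to ordinary adjusted regression on lesion rows. The planned crude t-test gives lower figures, and the plan does not say that lesions would be the rows.

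**Conclusion.** The point holds as a should-fix on secondary analyses. The data decide whether the adjusted result for four formally tested endpoints is shown, and no other section cures this.

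With one value per patient the crude tests are valid but conservative: size about 4% and about 2 points of power lost at R2 0.1; about 3% and 7 to 8 points at R2 0.3; and no loss at R2 0, where adjustment itself costs about 0.5 point. For maximum pressure the conservatism is not assured. If lesions were rows, crude size would be about 5 to 7% at R2 0.1 and 4 to 6% at R2 0.3, for within-patient correlation of 0.3 to 0.7.

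R2, its split between site and factors, effect size, block size, graft share and correlations are all assumptions. The text-based part of the finding (conditional reporting, no stated unit, unnamed fallback) needs none of them.

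**What to change.** 1. In section 11.3.2, delete the significance condition on reporting. Report crude and adjusted treatment differences with 95% confidence intervals whatever the result. In section 11.3.3, report the exploration of the stratification variables regardless of its outcome.
2. For each of the four endpoints, pre-specify one regression on treatment, lesion number, access type and site. Its one-sided treatment p-value enters Holm, with the crude t-test as supportive. Pool sites with fewer than 10 patients into one category, because section 11.1 sets no minimum enrolment.
3. Analyse maximum pressure as one value per patient: the highest across that patient's study lesions.
4. Remove the data-driven fallback. Fix in advance which p-value enters Holm for each endpoint: for example, regression on ranks for procedural cost, and linear regression with robust standard errors for pain, time and maximum pressure. For cost, give the adjusted mean difference with a robust 95% interval as descriptive only, since ranks and means address different hypotheses.

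The cost is SAP wording. All the adjustment factors are known at randomisation, so no patients or data are added. The downside is up to 9 degrees of freedom for site, about 0.5 point of power if the factors explain nothing. The primary test is unchanged.
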